13.2. Appendix 2: Study Phases and Treatment Emergent Adverse Events

13.2.1. Study Phases for Concomitant Medication

Study Phase	Definition
Prior	If medication end date is not missing and is before the first exposure date to study drug
Concomitant	Any medication that is not a prior. Note that medications with partial or missing start and/or stop dates will be assumed to be concomitant unless there is evidence through comparison of partial dates to suggest otherwise.

13.2.2. Treatment Emergent Flag for Adverse Events

Flag	Definition
Treatment	If AE onset date is on or after treatment start date, having been absent pre-
Emergent	treatment, or the AE worsens relative to the pre-treatment state.

NOTES:

- Time of study treatment dosing and start/stop time of AEs should be considered, if collected.
- Worsening of an event is captured in the eCRF by modifying the severity of the original event; therefore, worsening is accounted for in how the AE is recorded and no programming is required to identify worsening events.

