8.9.1. Time Period and Frequency for Collecting AE and SAE Information

- All SAEs will be collected from the start of treatment until the follow-up visit at the time points specified in the SoA (Section [1.3](#)). However, any SAEs assessed as related to study participation (e.g., study intervention, protocol-mandated

procedures, invasive tests, or change in existing therapy) or related to a GSK product will be recorded from the time a participant consents to participate in the study.

- All AEs will be collected from the start of treatment until the follow-up visit in Part B of the study at the time points specified in the SoA (Section 1.3).
- Medical occurrences that begin before the start of study intervention but after obtaining informed consent will be recorded on the Medical History/Current Medical Conditions section of the CRF, and not within the AE section.
- All SAEs will be recorded and reported to the sponsor or designee immediately and under no circumstance should this exceed 24 hours, as indicated in [Appendix 3](#). The investigator will submit any updated SAE data to the sponsor within 24 hours of it being available.
- Investigators are not obligated to actively seek AEs or SAEs after the conclusion of the study participation. However, if the investigator learns of any SAE, including a death, at any time after a participant has been discharged from the study, and he/she considers the event to be reasonably related to the study intervention or study participation, the investigator must promptly notify the sponsor.

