10.3.1. Definition of AE

AE Definition

• An AE is any untoward medical occurrence in a clinical study participant, temporally associated with the use of a study intervention, whether or not considered related to the study intervention.• NOTE: An AE can therefore be any unfavorable and unintended sign (including an abnormal laboratory finding), symptom, or disease (new or exacerbated) temporally associated with the use of a study intervention.

Events Meeting the AE Definition

• Any abnormal laboratory test results (hematology, clinical chemistry, or urinalysis) or other safety assessments (e.g., ECG, radiological scans, vital signs measurements), including those that worsen from baseline, considered clinically significant in the medical and scientific judgement of the investigator (i.e., not related to progression of underlying disease).• Exacerbation of a chronic or intermittent pre-existing condition including either an increase in frequency and/or intensity of the condition.• New conditions detected or diagnosed after study intervention administration even though it may have been present before the start of the study.• Signs, symptoms, or the clinical sequelae of a suspected drug-drug interaction.• Signs, symptoms, or the clinical sequelae of a suspected overdose of either study intervention or a concomitant medication. Overdose per se will not be reported as an AE/SAE unless it is an intentional overdose taken with possible suicidal/self-harming intent. Such overdoses should be reported regardless of sequelae.• The signs, symptoms, and/or clinical sequelae resulting from lack of efficacy will be reported as AE or SAE if they fulfill the definition of an AE or SAE. Also, "lack of efficacy" or "failure of expected pharmacological action" constitutes an AE or SAE.

Events NOT Meeting the AE Definition

• Any clinically significant abnormal laboratory findings or other abnormal safety assessments which are associated with the underlying disease, unless judged by the investigator to be more severe than expected for the participant's condition.

- The disease/disorder being studied or expected progression, signs, or symptoms of the disease/disorder being studied, unless more severe than expected for the participant's condition.
- Medical or surgical procedure (e.g., endoscopy, appendectomy): the condition that leads to the procedure is the AE.

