5.4. Baseline Definitions

For all endpoints, the baseline value will be the latest pre-dose assessment with a non-missing value, including those from unscheduled visits. If time is not collected, Day 1 assessments are assumed to be taken prior to first dose and used as baseline.

Parameter	Study Assessments Considered as Baseline		Baseline Used in Data Display		
	Screening	Day 1 (Pre-Dose)			
Efficacy					
SELENA-SLEDAI	X	X	Day 1		
Safety and Biomarker					

Parameter	Study Assess	Baseline Used in Data Display	
	Screening	Day 1 (Pre-Dose)	
Laboratory assessments (including hematology, urinalysis, chemistry, AntidsDNA/ANA and complement C3/C4)	X	X	Day 1
Biomarkers (including BLyS Protein, B-Cells, and immunogenicity)		X	Day 1

Note that the SELENA-SLEDAI total score is calculated by summing 24 individual items. The total score used as Baseline will be calculated from all available items at Day 1, but if individual items are missing, the Screening assessment for those items will be used.

Concomitant medications are considered to be present at baseline if the start date is prior to Day 1 and the end date is on or after Day 1. Medications with a start date on Day 1 are considered as being on-treatment (concomitant). For further details, see Section 13.2.1.

Adverse events (AE) are considered pre-treatment if the start date is prior to Day 1, or if the start date is on Day 1 but the AE start time shows that the event starts pre-dose. Treatment emergent AEs are defined in Section 13.2.2.

Unless otherwise stated, if baseline data is missing no derivation will be performed and baseline will be set to missing.

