8.1. Secondary Endpoint - Adverse Events

8.1.1. Adverse Events Analyses

Adverse events analyses including the analysis of adverse events (AEs), Serious adverse events (SAEs) and AEs of special interest (AESIs) will be based on GSK Core Data Standards. All subjects will be followed for safety up to 16 weeks post-treatment.

All AEs will be classified using the current standard GSK Medical Dictionary for Regulatory Activities (i.e. MedDRA version in use at the time of reporting), and grouped by System Organ Class (SOC) and/or Preferred Term (PT). The MedDRA version is detailed on every table that uses MedDRA. The investigator will evaluate all AEs with respect to seriousness, severity and causality. The severity of an AE is to be determined using the Assessment of Intensity provided in Appendix 2 of the protocol, if a grade is provided for the AE of interest.

For the following summaries, only treatment-emergent AEs will be summarized, unless otherwise stated. Treatment-emergent AEs are defined in Section 13.2.2 based on start date/time of AE versus first dose date/time of study treatment. AEs with missing start and/or stop dates will be assumed to be treatment-emergent.

The duration of the AE will be calculated as follows:

Duration of AE (days) = Date of AE resolution – AE start date + 1.

If the AE is ongoing the duration will be left blank and no imputation will be done.

Common non-serious AEs will be defined as two or more subjects experiencing the event.

An overall summary of AEs will be presented showing the number and percentage of subjects with at least one: AE, related AE, SAE, severe AE, SAE and/or severe AE, AE resulting in study agent discontinuation and death [T3.01].

The number and percentage of subjects experiencing an AE will be summarized for each of the following AE categories:

- All AEs (by SOC and PT; by PT only) [T3.02, T3.03]
- All SAEs (by SOC and PT) [T3.04]
- AEs resulting in study agent discontinuation (by PT only) [T3.05]
- Common non-serious AEs (number of subjects and occurrences) (by SOC and PT) [T3.06]
- SAEs (number of subjects and occurrences) (by SOC and PT) [T3.07]
- Study drug related Non-Serious AEs (by PT only) [T3.08]
- Study drug related fatal and non-fatal SAEs (by PT only) [T3.09]
- AEs by severity (by SOC and PT) [T3.10]
- Study drug related AEs by severity (by SOC and PT) [T3.11]

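### SAP 13.2.2 counts worsened pre-dose adverse events as treatment-emergent, but no rule applies this, so the few AE records with pre-dose onset that worsen after dosing miss the summary tables

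*SAP*

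**What the plan says.** SAP 13.2.2 defines the treatment-emergent flag in two limbs. The text breaks inside a hyphenated word: "If AE onset date is on or after treatment start date, having been absent pre", continuing "treatment, or the AE worsens relative to the pre-treatment state". The first limb is new onset after treatment start. The second is worsening of something already there.

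The second note to that definition explains how worsening is handled: "Worsening of an event is captured in the eCRF by modifying the severity of the original event". It concludes that "worsening is accounted for in how the AE is recorded and no programming is required to identify worsening events".

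Two other SAP sections say how events are classified:

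- Section 8.1.1: "Treatment-emergent AEs are defined in Section 13.2.2 based on start date/time of AE versus first dose date/time of study treatment". The same section limits the AE summaries to treatment-emergent events unless stated otherwise.
- Section 5.4: "Adverse events (AE) are considered pre-treatment if the start date is prior to Day 1". It adds Day 1 events whose start time falls before the dose.

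The protocol decides which pre-dose events have an AE record at all. Section 8.9.1 starts general AE collection at the start of treatment. Occurrences between consent and first dose "will be recorded on the Medical History/Current Medical Conditions section of the CRF, and not within the AE section". The exception is SAEs judged related to taking part in the study or to a sponsor product, which are recorded from consent. Section 10.3.1 lists among events that are AEs: "Exacerbation of a chronic or intermittent pre-existing condition including either an increase in frequency and/or intensity of the condition".

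**The concern.** The note does not deliver what the definition promises. It reasons that because severity is changed on the existing record, nothing further is needed to find worsened events. But the flag is set from the start date and time, and editing severity leaves these unchanged. A record that began before first dose stays pre-treatment however much it worsens afterwards.

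Incidence of AEs and SAEs through Week 52 is the secondary safety endpoint. For the records concerned, the error runs in one direction: an event that the SAP's own definition counts is missing from the treatment-emergent tables in 8.1.1 (T3.01 to T3.11).

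**Working it through.** The plan gives no figure to reproduce here, so the check is a comparison of the rules, followed by a scale for one child.

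**Step 1. Does any rule apply the worsening limb?**

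| Source | What it uses | Pre-dose AE record, severity raised after first dose |
|---|---|---|
| SAP 13.2.2, definition | onset, or worsening from before treatment | treatment-emergent |
| SAP 13.2.2, second note | severity changed on the same record, no derivation | start date unchanged |
| SAP 8.1.1 | start date/time against first dose | not treatment-emergent |
| SAP 5.4 | start before Day 1, or before the dose on Day 1 | pre-treatment |

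The definition gives one answer, and the rules that classify the record give the other. Protocol 10.3.3 also puts new information on the CRF already completed, which agrees with editing one record and not opening a second.

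**Step 2. Which events can have an AE record with pre-dose onset?**

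- *Ordinary conditions and non-serious events between consent and first dose.* Protocol 8.9.1 sends them to Medical History, so there is no AE record to edit. Under 10.3.1 their exacerbation is an AE. Since AE collection starts with treatment, the natural entry is a new AE with on-treatment onset, which the start-date rule counts.
- *Study- or product-related SAEs from consent.* These are recorded as SAEs before first dose, so they are exposed to the gap.
- *Other pre-dose events that reach the AE page*, for example a Day 1 event starting before the injection. The protocol does not call for such records, but SAP 5.4 has a class for them. They are exposed if they exist.

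The schedules of activities mark adverse events at screening, but their footnote refers back to 8.9.1, so the mark does not widen the set.

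**Step 3. How large is one omission?**

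Input: about 28 treated children (Protocol 9.2).

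- Weight of one child in an incidence = 100 / 28 = 3.6 percentage points.

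The number of exposed records is not in the documents, so no expected effect can be computed. To change the overall AE rate, a child would need a study- or product-related SAE (or a misfiled event) before any dose, would still have to be enrolled and dosed, would have to worsen afterwards, and would need to have no other treatment-emergent AE. For a preferred-term row, the last condition applies only within that term.

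**Step 4. Are the records lost from the report?**

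No. L3.01 lists all AEs by subject and L3.03 all SAEs. Neither is described as restricted to treatment-emergent events.

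**The case against.** The strongest reply is that the protocol has already dealt with the problem. A reader of 13.2.2 alone might infer that any pre-dose condition made worse on belimumab drops out of the tables. In children with active lupus and up to 35 days of screening, that would be serious. The documents do not support this. Such conditions are in Medical History, and their exacerbation is an AE in its own right. Expected progression of lupus is not an AE unless more severe than expected (Protocol 10.3.1). This objection stands and limits the point to the exposed set in Step 2.

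One part of it is inference. No section says outright that a worsened medical-history condition is entered as a new AE dated at worsening. Read literally, the first limb of 13.2.2 also excludes it, because the condition was not absent before treatment; only the start-date rule in 8.1.1 lets it in. That supports clarifying the text, but it does not show that events are lost.

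Two further inferences should be resisted:

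- *That several children are affected, costing several percentage points.* Nothing in the documents supports a count.
- *That the by-injection tables T3.13 to T3.17 are wrong because a reaction that worsens later stays at its first injection.* Those tables do not use severity, and assigning a continuous event to the injection at onset is a legitimate convention. The SAP also does not say whether a dated severity history is kept, so loss of the worsening date is not established.

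**Conclusion.** The inconsistency within the SAP is real: the definition has a worsening limb that its own note and the classification rules in 8.1.1 and 5.4 leave without effect. The consequence is confined to AE-page records with pre-dose onset that worsen on or after first dose. The number is unknown and probably very small.

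This rests on two assumptions: that sites follow Protocol 8.9.1 in filing pre-dose events, and that they open a new AE when a medical-history condition worsens. More misfiling would enlarge the exposed set. Severity is minor: a clarification that makes the safety endpoint match its stated definition.

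**What to change.** Replace the second note in SAP 13.2.2 with two statements:

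1. Worsening of a medical-history condition on or after first dose is a new AE, with onset at the date of worsening.
2. Any AE or SAE record with onset before first dose whose severity increased on or after first dose is flagged treatment-emergent.

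Align 5.4 and 8.1.1 so that the start-date rule carries the same exception.

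A change of wording alone will not reach data already entered: screening began in November 2019, and this SAP follows the December 2022 amendment. Before the first database lock, list the AE records with pre-dose onset and have sites confirm whether and when each worsened. The eCRF edit date should not stand in for this. It shows when a field was changed, so a later query correction could be counted as worsening.

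T3.13 to T3.17 need no change. The cost is a text edit, a small manual review, and possibly a slightly higher reported incidence.

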13.3. Appendix 3: Data Display Standards & Handling Conventions

13.3.1. Reporting Process

Software					
The currently sup	The currently supported versions of SAS software will be used (version 9.4 or higher).				
Reporting Area					
HARP Server	: us1salx00259				
HARP Compound	: gsk1550188				
Study location	: gsk1550188\mid200908				
Analysis Datasets	Analysis Datasets				
 Analysis datasets will be created according to CDISC standards (SDTM IG Version 3.2 & ADaM IG Version 1.1). 					
Generation of RTF Files					
RTF files will be generated for all tables.					

13.3.2. Reporting Standards

General

- The current GSK Integrated Data Standards Library (IDSL) will be applied for reporting, unless otherwise stated (IDSL Standards Location:
 - https://spope.gsk.com/sites/IDSLLibrary/SitePages/Home.aspx):
 - 4.03 to 4.23: General Principles
 - 5.01 to 5.08: Principles Related to Data Listings
 - 6.01 to 6.11: Principles Related to Summary Tables
 - 7.01 to 7.13: Principles Related to Graphics

Formats

- GSK IDSL Statistical Principles (5.03 & 6.06.3) for decimal places (DP's) will be adopted for reporting of data based on the raw data collected, unless otherwise stated.
- Numeric data will be reported at the precision collected on the eCRF.
- The reported precision from non eCRF sources will follow the IDSL statistical principles but may be adjusted to a clinically interpretable number of DP's.

Planned and Actual Time

- Reporting for tables, figures and formal statistical analyses:
 - Planned time relative to dosing will be used in figures, summaries, statistical analyses and calculation of any derived parameters, unless otherwise stated.
 - The impact of any major deviation from the planned assessment times and/or scheduled visit days on the analyses and interpretation of the results will be assessed as appropriate.
- Reporting for Data Listings:
 - Planned and actual time relative to study drug dosing will be shown in listings (Refer to IDSL Statistical Principle 5.05.1).
 - Unscheduled or unplanned readings will be presented within the subject's listings.

Unscheduled Visits

All unscheduled visits will be included in listings.

CONFIDENTIAL

Descriptive Summary Statistics				
Continuous Data	Refer to IDSL Statistical Principle 6.06.1			
Categorical Data	N, n, frequency, %			
Graphical Displays				
Refer to IDSL Statistical Principals 7.01 to 7.13.				

13.4. Appendix 4: Derived and Transformed Data

13.4.1. General

Multiple Measurements at One Analysis Time Point

- For continuous data, if there are two values within a time window (as per Section 13.1.1) the value closest to the target day for that window will be used. If values are the same distance from the target, then the mean will be taken. All data will be presented in the listings.
- For categorical data, if there are two values within a time window (as per Section 13.1.1) the value closest to the target day for that window will be used. If values are the same distance from the target, then the value prior to the target day will be taken. All data will be presented in the listings.
- Participants having both High and Low values for Normal Ranges at any post-baseline visit for safety parameters will be counted in both the High and Low categories of "Any visit post-baseline" row of related summary tables.

Study Day

- Calculated as the number of days from First Dose Date:
 - Ref Date = Missing → Study Day = Missing
 - Ref Date < First Dose Date → Study Day = Ref Date First Dose Date
 - Ref Date ≥ First Dose Date → Study Day = Ref Date First Dose Date + 1

Study Completion

- A participant is considered to have completed the primary study if he/she has completed all phases during Parts A and B of the study, including the Week 52 Visit, as defined in the Schedule of Activities (SoA) Section 1.3 of the protocol.
- A participant is considered to have completed Part A of the study if he/she has completed all 12
 weeks of the treatment phase, including the Week 12 Visit, as defined in the SoA (see Section 1.3 of
 the protocol).
- Participants who withdraw from study treatment prior to the end of Part A and participants who
 complete Part A but do not wish to continue into Part B are required to complete 8 and 16 week
 follow-up visits.
- Participants who withdraw from treatment prior to Week 12, should complete an early withdrawal (EW) visit, in addition to the 8 and 16 week follow-up visit and assessments. The EW visit requires identical assessments and procedures to the Week 12 (Day 85/81) visit.
- Participants who withdraw from treatment prior to Week 52, should complete an EW visit, in addition to the 8 and 16 week follow-up visit and assessments. The EW visit requires identical assessments and procedures to the Week 52 visit.

